## **6.7.2 Dose Limiting Toxicities**

Dose-limiting toxicities will include any NCI CTCAE v.5 Grade 3 or higher adverse reaction occurring within 4 weeks following the administration of M254.

**Note:** Events considered by the sponsor as clearly unrelated to the study drug will not be considered a DLT, eg, thrombocytopenia related to ITP, accidents, and lab results attributed to other therapies or illnesses.

# 6.7.3 Rules for Dosing Adjustments, Withholding or Restarting, Permanent Discontinuation

Unless participant safety precludes doing so, the Medical Monitor should be consulted prior to stopping or modifying the dosing schedule of study drug.

Compound: M254 Protocol: MOM-M254-001

Protocol Date and Version:8 Global 28 April 2020

If more than 1 subject or patient with CTCAE Grade 3 or 4, not reasonably related to an alternative etiology (eg, motor vehicle accident-related injury or gunshot wound) the sponsor will discuss already collected data from the healthy subjects in Part A prior to discontinuation for the Part A (if already more than 1 dose level has been evaluated prior to the Part A being discontinued) with the Investigators and may modify other parts of the study as needed.

If 1 of the 2 ITP patients in Part B experiences any DLT, the cohort may be repeated with 2 additional ITP patients either at the same or lower dose per the recommendation of the SRC. If at a given dose level, 2 patients (either 2 of 2 or 2 of 4) experience a DLT that dose level will not be repeated, though a lower dose may be selected by the SRC.

## 6.7.4 Study Stopping Rules

Dosing in the study will be halted pending evaluation by Sponsor and SRC recommendation if one of the following circumstances occurs:

- Grade 5 AE considered related to study treatment, in which case the review process will also include regulatory agencies and IRBs/Ethics Committees
- The following Grade 3 or greater treatment-related AE in 2 or more patients:
  - thromboembolic AE
  - renal impairment AE
  - hemolysis AE
  - creatinine elevation

NOTE: Events that are definitely not related to study treatment (eg, accidents or other external causes) will not trigger study-stopping rules.

## 6.8 Intervention After the End of the Study

There is no intervention planned after participants complete the study.

# 7 DISCONTINUATION OF STUDY INTERVENTION AND PARTICIPANT DISCONTINUATION/WITHDRAWAL

## 7.1 Discontinuation of Study Intervention

In accordance with the Declaration of Helsinki, International Council for Harmonisation (ICH) GCP Guidelines, and the US FDA Regulations, a research subject has the right to withdraw at any time for any reason without prejudice to future medical care. However, in the absence of a medical contraindication, the Investigator should encourage the subject to remain in the study and, at a minimum, follow the subject for safety data collection.

Compound: M254 Protocol: MOM-M254-001

Protocol Date and Version:8 Global 28 April 2020

The Sponsor and Investigator also have the right to withdraw participants. Subjects or patients may be discontinued from study treatment if they experience intolerable toxicity related to any study treatment despite dose reduction, or for any of the following reasons:

- Withdrawal of subject informed consent
- AE
- Significant noncompliance with protocol requirements
- Need for prohibited therapy
- Termination of the study
- Any other reason which, in the opinion of the Investigator or Sponsor, would justify the subject's removal
- Subject lost to follow-up

All reasons for early termination or withdrawal will be documented in the eCRF.

The Sponsor and the Investigator may decide to halt dosing for safety reasons, including emerging nonclinical data, clinically relevant AEs, or relevant data from other sources indicating safety concerns.

Termination of the study by the Sponsor may take place upon written notice to PRA Netherlands for the following reasons: 1) if the Ethics Committee irrevocably revokes approval for the study; 2) if it is necessary to protect the safety, health, or welfare of participants; 3) if it transpires that continuation of the study cannot serve any scientific purpose, and this is confirmed by the Ethics Committee; 4) if conducting the study becomes prohibitive by law, rule, regulation, or any amendment thereof; or 5) if the Investigator is no longer capable of performing the tasks of the Investigator, and no replacement agreeable to both parties can be found.

## 7.2 Discontinuation/Withdrawal From the Study

A participant may withdraw from the study at any time at his/her own request, or may be withdrawn at any time at the discretion of the Investigator for safety, behavioral, compliance, or administrative reasons. This is expected to be uncommon.

An Investigator may discontinue or withdraw a participant from the study for the following reasons:

- Any treatment-related Grade 3 or higher AE per NCI CTCAE version 5.0 criteria
- Pregnancy (see Appendix 4 and Section 8.4.5)
- If in the opinion of the Investigator, patient with ITP is not responding adequately or for adequate duration in Part D (ie, no platelet count increase from baseline or return to

Compound: M254 Protocol: MOM-M254-001

Protocol Date and Version:8 Global 28 April 2020

baseline within 1 weeks), subject should be discontinued from the study to timely administer treatment per local standard of care.

- Protocol deviation
  - Noncompliance to intervention
  - Requires treatment not allowed in the protocol for disease flare
  - If the participant meets an exclusion criterion (either newly developed or not previously recognized) that precludes further study participation
- Sponsor decision
- Participant request to discontinue study intervention

At the time of discontinuing from the study, if possible, an early discontinuation visit should be conducted, as shown in the Schedule of Activities (Section 1.2). See activities for the final follow-up to be performed.

The participant will be permanently discontinued both from the study intervention and from the study at that time.

If the participant withdraws consent for disclosure of future information, the sponsor may retain and continue to use any data collected before such a withdrawal of consent.

If a participant withdraws from the study, he/she may request destruction of any samples taken and not tested, and the Investigator must document this in the site study records.

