## 4.1.4 Part D (USA sites included)

Part D is a repeated, fixed-dose, open-label study of M254. Any patients who participate in Parts B or C are allowed to participate in Part D if they meet inclusion criteria during screening for Part D. Part D may have up to 2 dose levels with up to approximately 15 to 34 ITP patients in total. The initial dose level for Part D will be less than or equal to the maximum tolerated dose, and it will be selected based on review of Part B data and available data from Part C. Following completion of Part C, the dose for new patients in Part D may be revised (the dose level will not be modified for patients who have already received at least 1 dose). Patients who have participated in Part B or C may be allowed to participate in Part D, prior to completion of randomization in Part C. New patients not in Part B or C may participate in Part D following complete randomization in Part C. The dose levels of M254 for Part D will be determined after analysis of available data from Part A, Part B, and Part C.

Following screening to confirm eligibility to participate (including rescreening patients who participated in Part B or C), M254 naïve patients will receive 4 doses of M254, and patients from Part B or C will receive 3 doses of M254 every 14 days. Patients in Part C may roll over into Part D by including any data after the last dose of IVIg or M254 in Part C for assessment of screening in Part D as long as those data are within the screening window specified. Please refer to Section 4.3.1 and Figure 1-5 for dosing details.

If the patient's platelet count has not returned to  $\leq 100 \times 10^9 / L$ , their platelet count will be monitored weekly until platelets return to  $\leq 100 \times 10^9 / L$ . If these conditions are not met, M254 will not be administered further. Patients will be followed for safety assessments and platelet counts up to at least 28 days post their last dose of M254. Safety will be reviewed by the SRC quarterly (or more often as required).

Blood for safety labs, PK, and PD will be collected as defined in the Schedule of Activities (Table 1-4).

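### Part D: Protocol 7.2 takes inadequate responders out of the study, so scheduled collection of new AEs, labs and platelets can stop short of the 28 days that 4.1.4 requires

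*Protocol*

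**What the plan says.** Section 4.1.4 sets the Part D rule: "Patients will be followed for safety assessments and platelet counts up to at least 28 days post their last dose of M254". It names no exception. The same section describes one kind of M254 stop, for patients whose platelets do not fall to 100 × 10⁹/L or below: "If these conditions are not met, M254 will not be administered further". Those patients remain under the follow-up rule.

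Section 7.2 lists reasons for which an Investigator may withdraw someone from the study. One is specific to Part D. If, in the Investigator's opinion, platelets have not risen from baseline, or have gone back to baseline within a week, the "subject should be discontinued from the study to timely administer treatment per local standard of care". Two other listed reasons are "Participant request to discontinue study intervention" and "Requires treatment not allowed in the protocol for disease flare". The section then provides for one early discontinuation visit, where possible, using the final follow-up activities, and adds: "The participant will be permanently discontinued both from the study intervention and from the study at that time".

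Section 7.1, on stopping study drug, says that absent a medical contraindication the Investigator should "encourage the subject to remain in the study and, at a minimum, follow the subject for safety data collection". Its own reasons for stopping treatment include "Need for prohibited therapy".

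Section 8.4.1 puts no duty on Investigators to look for new AEs or SAEs once participation has ended.

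**The concern.** The purpose given in the inadequate-response bullet is prompt local treatment. Stopping M254 achieves that, but the bullet ends study participation instead. A site that follows it literally does not deliver the follow-up in 4.1.4.

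The data at risk serve a Part D primary endpoint: incidence and severity of AEs, and clinically significant laboratory changes, with repeated dosing (3.4). The synopsis says the 28-day monitoring period was chosen deliberately. Section 6.7.2 defines dose-limiting toxicity over four weeks. Section 8.3.5 says most delayed infusion reactions come 5 to 10 days after the infusion, so an exit at about day 7 falls inside that window.

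Follow-up length would also depend on platelet response, which is the drug's own effect. SAP 9.1.4 and 9.5 summarise Part D by actual number of doses, and SAP 9.1.3 bases percentages on subjects exposed. Neither allows for time observed. Within one actual-dose group, a patient stopped for high platelets is followed for at least 28 days, and one stopped for lack of response perhaps for 7. Each counts as one exposed subject.

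**Working it through.** **Inputs.** Dose days are 1, 15, 29 and 43 for M254-naïve patients and 1, 15 and 29 for Part B/C patients. One-week visits are Days 8, 22, 36 and 50 (±1). Final follow-up is Day 71 or Day 57 (±3). All come from Table 1-4 and Table D2. The 28-day minimum is in 4.1.4. The exit day is an assumption, because the documents do not fix it.

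**1. The plan's own figure.** Final follow-up minus last dose:
- Naïve: 71 − 43 = 28 days.
- Part B/C: 57 − 29 = 28 days.

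The schedule reproduces the 28 days nominally (25 to 31 with the ±3-day window).

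**2. Days lost per exit.**

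| Assumed exit | Days after last dose | Days lost | Share of 28 |
|---|---|---|---|
| One-week visit | 7 | 28 − 7 = 21 (20 to 22 with ±1 day) | 75% |
| Next dosing visit | 14 | 28 − 14 = 14 | 50% |
| Site keeps following under 7.1 and 4.1.4 | 28 | 0 | 0% |

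**3. What is missed after a day-7 exit.** Safety labs and platelets are due at 57 − 43 = 14 and 71 − 43 = 28 days after the last dose (naïve), and at 43 − 29 = 14 and 57 − 29 = 28 days (Part B/C). One early visit, where possible, stands in for both.

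**4. Weight of one 21-day loss in the whole of Part D (15 to 34 patients).**
- Against planned post-last-dose days: 21/(15 × 28) = 5.0%; 21/(34 × 28) = 2.2%.
- Against all planned observation from Day 1 (71 − 1 = 70 days naïve, 57 − 1 = 56 days Part B/C): 21/(15 × 70) = 2.0% and 21/(15 × 56) = 2.5%; 21/(34 × 70) = 0.9% and 21/(34 × 56) = 1.1%.

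These are per exit. The number of exits cannot be derived from the documents.

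**5. The texts side by side.** A patient who stops M254 for persistently high platelets stays under the 28-day rule. A patient who stops because M254 did not work is told to leave. Needing a therapy the protocol does not allow is a reason to stop drug in 7.1, while 7.2 makes much the same need a reason to leave the study.

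**6. Are follow-up visits already scheduled for early stoppers?** Days 14 and 28 after a mid-course dose fall on:
- Naïve: Days 15 and 29 (after dose 1), 29 and 43 (dose 2), 43 and 57 (dose 3).
- Part B/C: Days 15 and 29 (dose 1), 29 and 43 (dose 2).

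Eight of these ten are infusion visits; only naïve Day 57 and Part B/C Day 43 are not. A non-dosing version therefore has to be stated.

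**The case against.** The strongest reply is 7.1. It already tells the Investigator to encourage staying and, at the least, to follow for safety. It sits under the heading on stopping study drug, so it speaks directly to someone who asks only to stop drug. The 7.2 list opens with a permissive verb, the response judgement is the Investigator's, and 4.1.4 and 8.1.3 make no exception for early stoppers. A site could reasonably keep following. This stands to the extent that loss is possible rather than certain, and that the request-to-stop bullet is an ambiguity rather than a missing safeguard. It does not remove the conflict. The 7.1 sentence sets no schedule or duration, and once inadequate response is judged the 7.2 bullet says the patient should leave.

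Exit is also a defensible choice. Section 6.5 holds ITP medication at the screening dose. First-line treatment includes IVIg, from which M254 is made, so AEs after rescue IVIg are hard to attribute. That is fair, and it argues for showing later data separately rather than for not collecting them.

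The comparison within an actual-dose group is thin. High-platelet patients are monitored weekly and some will resume dosing. The SAP also pools doses for Part D safety tables. There is no formal testing, and disposition and study-date listings let a reader see each patient's follow-up. This is right, although no summary adjusts for follow-up time.

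A reader might infer that any drug stop, in any part, forces study exit. The sentence ending both together does not support that: read alone, it may cover only people already leaving. A reader might also infer that safety information ceases at exit. It does not. Sections 8.3.1 and 8.4.3 continue follow-up of related AEs, SAEs and AEs of special interest already reported, and 8.4.1 still requires prompt notice of a later SAE that the Investigator learns of and considers related.

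**Conclusion.** The concern holds in a limited form. For Part D inadequate responders, 7.2 conflicts with 4.1.4 and 7.1, and a site that follows 7.2 as written will stop scheduled collection of new AEs, labs and platelets early. The request-to-stop-drug bullet needs the same clarification.

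The loss per exit is about 21 of 28 days if exit is at the one-week visit, 14 if at the next dosing visit, and 0 if the site keeps following. These figures rest on the assumed exit day. The number of patients is unknown, and 7.2 expects withdrawal to be uncommon, so the documents do not show that Part D safety results would be materially distorted. This is a correctable gap in primary safety data that is worth closing, and it does not invalidate the design.

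**What to change.** For Part D only:

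1. Reword the inadequate-response bullet so that the patient should be discontinued from M254 and may start local standard-of-care ITP treatment at once. Move it, and the bullet on asking to stop study drug, to 7.1.
2. Add to 7.2 that, unless consent is withdrawn, a Part D patient who stops M254 for these reasons stays in safety follow-up (AEs, concomitant medications, safety labs, platelets). State that this includes a patient who starts local ITP treatment, so that the bullet on treatment the protocol does not allow no longer forces exit for these patients. Specify non-dosing visits about 14 and 28 days after the last dose, the second with the final follow-up procedures.
3. Record the start date of any new ITP therapy. In SAP 18.1.1, show AEs starting after that date separately. In SAP 17.1.2, keep later platelet counts out of the Table 2 parameters.

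The sentence that ends drug and study together covers all parts, and nothing here requires changing it for Parts A to C.

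The cost is a few lines of protocol and SAP text and one or two more visits per such patient, with procedures already in the plan. Table D2 footnote d lets visits other than screening, infusions, the day after an infusion and the last follow-up be done by visiting nurse, so the day-14 visit could be. The downside is that data after a new therapy starts are confounded by it, most of all after rescue IVIg.

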## 7.3 Lost to Follow-up

A participant will be considered lost to follow-up if he or she repeatedly fails to return for scheduled visits and is unable to be contacted by the study site.

The following actions must be taken if a participant fails to return to the clinic for a required study visit:

- The site must attempt to contact the participant and reschedule the missed visit as soon as possible and counsel the participant on the importance of maintaining the assigned visit schedule and ascertain whether or not the participant wishes to and/or should continue in the study.
- Before a participant is deemed lost to follow-up, the Investigator or designee must make every effort to regain contact with the participant (where possible, 3 telephone calls and, if necessary, a certified letter to the participant's last known mailing address or local equivalent methods). These contact attempts should be documented in the participant's medical record.
- Should the participant continue to be unreachable, he/she will be considered to have withdrawn from the study.

Compound: M254 Protocol: MOM-M254-001

Protocol Date and Version:8 Global 28 April 2020

Discontinuation of specific sites or of the study as a whole are handled as part of Appendix 1.

#### 8 STUDY ASSESSMENTS AND PROCEDURES

Adherence to the study design requirements, including those specified in the Schedule of Activities (Section 1.2), is essential and required for study conduct.

## 8.1 General Study Periods

## 8.1.1 Screening, Enrollment, and/or Randomization

All patients must personally sign and date the IRB/IEC approved informed consent before any study-specific procedure can be performed. All screening evaluations (see Schedule of Activities [Section 1.2]) must be completed and reviewed to confirm that potential participants meet all eligibility criteria. The Investigator will maintain a screening log to record details of all participants screened and to confirm eligibility or record reasons for screening failure, as applicable. During screening, a complete medical history will be obtained from each subject/patient. Demographic data will also be collected in order to examine their possible association with patient safety and treatment effectiveness during initial screening.

Screening in Part B will proceed only when all single ascending dose cohorts in healthy volunteers up to 60 mg/kg have been reviewed for safety by the SRC, and if according to the Investigator and SRC, an interim summary of all safety data from Part A, through the 60 mg/kg cohort, concludes that the anticipated exposure in the first cohort of Part B does not impose unnecessary risk. The interim summary will be sent to the IEC, where required.

The SRC will review all safety data for all patients in Part B up to at least 28 days following M254 administration for the last patient. Initiation to Part C will only proceed on the recommendation of the SRC.

The SRC will review all safety data from both crossover cohorts in Part C; however, the initiation of Part D will proceed after the SRC reviews all safety database from Cohort 1 and the recommendation is to proceed with Part D with approval of the Investigator.

## 8.1.2 Treatment Period

Individual study assessments are presented in Schedule of Activities (Section 1.2). Where possible, a window for each study visit is described in the Schedule of Activities. Visit windows noted in the Schedule of Activities apply throughout all sections of the protocol. Subjects and patients should remain with a similar level of physical activity during the study and not initiate new or strenuous exercise from randomization to the final follow-up. Subjects and patients should be hydrated prior to the start of infusion with approximately 2 glasses of liquid to avoid a possible thromboembolic event. Additionally, subjects and patients should

Compound: M254 Protocol: MOM-M254-001

Protocol Date and Version:8 Global 28 April 2020

be mobilized immediately following the end of infusion to decrease the risk of thromboembolic events.

If 1 assessment in a series is missed, "not done" should be recorded in the clinic record and eCRF. The original schedule for postdose sample collection will be adhered to rather than adjusting the postdose scheduling from the point of the missed sample.

All collected data will be attributed to the closest nominal/scheduled time point for analysis; unscheduled assessments will be collected separately. The Sponsor does accept any institution-specific time allowances that are documented as part of the local standard operating procedures.

#### 8.1.3 Follow-up

A follow-up visit will be completed  $29 \pm 2$  days after the last dose of study drug for Parts A, B, and C. For Part D, the follow-up visit will be completed  $71 \pm 3$  days (M254 naïve patients) or  $57 \pm 3$  days (Part B/C patients). Refer to the Schedule of Activities (Section 1.2) for required procedures during this visit.

## 8.2 Efficacy Assessments

Efficacy endpoints are based on platelet levels and are collected at times described in the Schedule of Activities (Section 1.2).

## 8.3 Safety Assessments

Safety endpoints will be summarized using the Safety Analysis Set (SAF) and are collected at times described in the Schedule of Activities (Section 1.2).

Clinical significance for safety assessments is defined as any variation in assessment results that has medical relevance and may result in an alteration in medical care (eg, active observation, diagnostic measures, or therapeutic measures). If a clinically significant change from screening values is noted, the clinically significant value and reason for clinical significance will be documented on the AE page of the subject's eCRF. The Investigator will continue to monitor the subject with additional assessments until the values have reached reference range and/or the values at Screening, or until the Investigator determines that follow-up is no longer medically necessary.

### **8.3.1** Adverse Events

Adverse events will be assessed and recorded by the study staff. If an AE requires medical attention, it should be reported to the Investigator immediately. The Investigator must meet with the subject to assess all medical and psychiatric AEs reported by the subject, as well as those recorded by the study staff. After current AEs are assessed, the Investigator must review with the subject and assess any AEs unresolved from the previous assessment. After each AE assessment, the Investigator will record in the subject's source document and AE eCRF, according to the procedures described in Section 10.3, the type of AE and whether

Compound: M254 Protocol: MOM-M254-001

Protocol Date and Version:8 Global 28 April 2020

serious or nonserious, severity of each AE, and the relationship to the study agent. These categories are asking for the Investigator's best judgment of the severity and relatedness of each AE.

Any study subject with a related AE will be followed by the Investigator until the event is resolved to the satisfaction of the Site Investigator and Medical Monitor. During Part A, if the AE is unrelated, the subject will not be discharged until medically stable, and then will be referred, at the subject's sole expense, for ongoing care and/or treatment, which may include psychological and lifestyle counseling, support groups, or pharmacological and medical treatment.

Refer to Section 8.4 for information regarding AEs.

